**ABBREVIATIONS & DEFINITIONS**

AE	Adverse Event
ADE	Adverse Device Effect
BMI	Body Mass Index
CAPA	Corrective and Preventive Action
CFR	Code of Federal Regulations
CRF	Case Report Form
CRO	Contract Research Organization
CSR	Clinical Study Report
CV	Curriculum Vitae
DevD	Device Deficiency
EC	Ethics Committee
FAS	Full Analysis Set
FDA	Food and Drug Administration
GCP	Good Clinical Practice
ICH	International Conference on Harmonisation
ID	Identification
ISO	International Organization for Standardization
IRB	Institutional Review Board
KSS	Knee Society Score
PI	Principal Investigator
PP	Per Protocol
SAE	Serious Adverse Event
SADE	Serious Adverse Device Effect
SAP	Statistical Analysis Plan
SAS	Statistical Analysis System, SAS® Institute, Cary, NC
TKA	Total Knee Arthroplasty
UKR	Unicondylar Knee Replacement
USADE	Unanticipated Serious Adverse Device Effect

**Protocol Synopsis:**

Title of Study:	A Retrospective Study of the Navio ◊ Robotic-assisted Surgical System
Study Type:	Post-market
Study Device:	Navio ◊ Robotic-assisted Surgical System
Indications	Navio System-assisted Unicondylar Knee Replacements (UKR) are indicated for restoring either compartment of a knee that has been affected by: 
 
• Non-inflammatory degenerative joint disease including osteoarthritis, traumatic arthritis, or avascular necrosis
 
• Correction of functional deformity
 
• Treatment of fractures that are unmanageable using other techniques
 

Study design:	A retrospective, multi-center, cohort study with prospective follow-up and comparison to historical control
Primary Endpoint:	Navio System assisted Unicondylar Knee Replacement (UKR) revision rate 2 years postoperative
Secondary Endpoints:	Given the retrospective-prospective study design, secondary endpoint data will be collected to the extent that it is available and will include: 
 
• Change in Knee Society Score (KSS) from baseline to 2 years (-3months) or greater postoperative
 
• Change in VR12 from baseline to 2 years (-3months) or greater postoperative
 
• Anterior/Posterior and lateral radiographic assessments
 

Safety Assessment:	Study device and procedure-related adverse events (AE) incidence and frequency
Length of Study:	Up to 1 year: includes enrollment phase and collection of a minimum of 2-year postoperative follow-up data
Study Visits:	Retrospective pre-operative, operative and any available postoperative follow-up; Prospective 2-year or greater postoperative follow-up
Number of Sites:	Up to 10 sites in the United States and Europe
Sample Size:	One hundred twenty-eight (128) subjects, including 10% inflation to allow for attrition
Inclusion Criteria:	
 
1. Male or female subjects ≥18 years old (at the time of surgery) who have undergone Navio System-assisted UKR prior to IRB/EC site approval. This includes UKR procedures with all Unicondylar Knee cemented implant designs.
 
2. Subject had a primary diagnosis of unicompartmental, non-inflammatory degenerative joint disease including osteoarthritis, traumatic arthritis, or avascular necrosis, required correction of functional deformity, or required treatment of fractures that were unmanageable using other techniques.
 

Exclusion Criteria:	
 
1. Subject received the Navio System-assisted UKR on the index joint as a revision for a previously failed UKR.
 

	

2. Subject, in the opinion of the Investigator, had advanced osteoarthritis or joint disease at the time of surgery and was better suited for Total Knee Arthroplasty (TKA).

3. Subject, in the opinion of the Investigator, had a neuromuscular disorder that prohibited control of the index joint.

4. Subject, in the opinion of the Investigator, was morbidly obese.

5. Subject, in the opinion of the Investigator, was contraindicated for UKR.

6. Subject (prospective subjects only), in the opinion of the Investigator, has an emotional or neurological condition including mental illness, mental retardation, drug or alcohol abuse.

7. Subject (prospective subjects only) is a prisoner.

--	--

## 1. BACKGROUND AND STUDY RATIONALE

### 1.1. Background

Total Knee Arthroplasty (TKA) has become an effective and reliable treatment for arthritis of the knee (1). TKA is associated with low morbidity and mortality, and its effectiveness in reducing joint pain and improving range of motion is well established. In 2014, over 750,000 knee replacements were performed in the United States (2); it is estimated that 8-12% of these are Unicondylar Knee Replacements (UKR) (3).

UKR was first used in the 1970's and can be beneficial, as the UKR surgery preserves bone and ligaments, unlike many TKA systems. Recovery and rehabilitation are typically shorter (4). Initial revision rates as high as 30% over 6 years (5) led to proposed guidelines for patient selection (6). Resulting changes in the patient population, along with improvements in surgical technique have led to better outcomes and lower revision rates. A meta-analysis of 31 cohort studies published between 2000 and 2016 (7) reported annual revision rates by subgroup: males, 1.43%; females, 1.52%; age  $\geq$  60year, 1.45%; age  $<$  60year, 2.16%; Body Mass Index (BMI)  $<$  30, 0.79%; BMI  $\geq$  30, 0.91%.

A significant innovation in knee arthroplasty has been the introduction of computer navigation and robotic-assisted surgery (8). These technologies have improved the accuracy of bone preparation, implant positioning, and soft tissue balance in UKR and it is estimated that 15-20% of UKR surgeries in the United States are performed with robotic assistance (9). The Navio◊ Robotic-assisted Surgical System is a semi-autonomous image-free system. During the surgery, the surgeon maps the condylar landmarks and determines alignment indices to define the volume and orientation of bone to be removed. The tools to remove the bone and place the implants are controlled and manipulated by the surgeon with the guidance of a 3-dimensional digital map of the surgical surface. This system has been used in over 1000 UKR surgeries to date. The clinical effectiveness of the Navio System continues to be evaluated in the literature, and clinical studies are warranted to further evaluate the system.

This study is to be conducted according to US and international standards of Good Clinical Practice (GCP) including International Conference on Harmonisation (ICH) E6, the Code of Federal Regulation (CFR) and other applicable government regulations and institutional research policies and procedures.

## 2. STUDY OBJECTIVES

This clinical study will evaluate the 2-year safety and effectiveness of the Navio System in UKR in subjects  $\geq$  18years of age, as demonstrated by revision rate, changes in clinical, functional, and quality of life outcomes over time, radiographic assessments and Adverse Event (AE) incidence and frequency.

### 2.1. Primary Endpoint

Navio System assisted UKR revision rate 2 years postoperatively.

---

 Annual Revision Rate (%) =  $\frac{\text{Failures}}{\text{Observed component years}} \times 100$

Observed component years = Total observed knees  $\times$  Mean follow – up (years)

## 2.2. Secondary Endpoints

Given the retrospective-prospective study design, secondary endpoint data will be collected to the extent that it is available and will include:

- Change in Knee Society Score (KSS) from baseline to 2 years (-3months) or greater postoperative
- Change in VR12 from baseline to 2 years (-3months) or greater postoperative
- Anterior/Posterior and lateral radiographic assessments:
  - Radiographic findings
  - Component orientation
  - Radiolucencies
  - Migration
  - Osteolysis
  - Stress shielding
  - Subsidence

## 3. STUDY DESIGN

This is a retrospective, multi-center, cohort study with prospective follow-up and comparison to historical control to collect 2-year safety and effectiveness data on 128 subjects, at up to 10 sites in the United States and Europe, who have undergone Navio System-assisted UKR.

Subject data will be retrospectively evaluated at the pre-operative, operative, and any available postoperative follow-up visits as well as prospectively evaluated at the 2-year (-3months) or greater postoperative follow-up visit.

## 4. STUDY DEVICE

The Smith & Nephew Navio Robotic-assisted Surgical System aids the surgeon in planning and executing a procedure involving bone preparation for prosthesis implantation. The system is comprised of computer-assisted surgical instrument control, a commercially available surgical drill, image-free navigation, and planning software with standard navigation technology.

The Navio System uses data gathered during the beginning of the surgical procedure (planning phase) to generate a computer model of the knee surface to be remodeled in preparation for the implant. The software uses data collected during the planning phase along with pre-loaded data describing the implant geometry to guide the surgeon in shaping the knee for the selected implant. The Navio system software then allows the surgeon to evaluate the range of motion and fit of the implant prior to finalizing the procedure.

The Navio system software consists of a patient and user management module, a surgical planner, and an intraoperative cutting module. The surgeon uses patient data collected at the surgical site to align the implant and shape the target surface of the bone to accept the intended implant. The Navio system also uses the tracked position of the surgical bur to control its cutting engagement to the bone that is to receive the implant. This cutting control is based on the bur's proximity to the planned target surface of the bone.

The cutting control is achieved in two ways:

- Exposure control adjusts the bur's exposure with respect to a guard. If the surgeon encroaches on a portion of bone that is not to be cut, the Navio system retracts the spinning bur behind the guard, disabling cutting. The Navio system software also adjusts the depth of the cut by adjusting the exposure of the bur outside of the bur guard.
- Speed control regulates the signal transmitted to the drill motor. This limits the speed of the spinning bur or disables bur motion entirely if the target surface has been reached. Bur motion is also disabled if the bur is moved outside of expected cutting boundaries.

The surgeon can alternate between these two cutting control modes. The surgeon can also disable both cutting control modes and operate the Navio system as a standard navigated drill.

The Navio system incorporates a detailed user interface that provides procedure setup, tracking status, visual indicators, and real-time cutting progress during the procedure.

The Navio System is shown below:

Description	Part Number
Tracking Camera and Stand	110001
Navio System Cart	NPFS-02000, -02010, -02020, -02070
Anspach Drill Foot Control	120041
Navio System Foot Control	100460
Navio System Handpiece	110137
Anspach Drill	101209

The function of each component is as follows:

- Tracking Camera and Stand - The mobile infrared tracking camera is used to determine the position of the point probe and the surgical bur tip and track their movement by scanning the position of reflective trackers relative to the position of trackers mounted on the patient's femur and tibia.
- Navio System Cart - The mobile cart contains the electronic control system, electrical system integration unit, computer, and uninterruptible power supply (UPS). Navio system carts are available in 120 VAC and 220-240 VAC versions. The cart provides storage for the power cord, Anspach◊ drill foot control, and the Navio system foot control. The touchscreen monitor is the primary user interface for the Navio system.
- Anspach◊ Drill Foot Control - The Anspach drill foot control is used to control the Anspach drill during surgery. The surgeon must press the foot control to activate the bur. The speed of the bur is controlled by the Navio system software in speed control mode.
- Navio System Foot Control - The Navio system foot control is used as an alternative to the touchscreen monitor when data points are being collected to define landmarks, shape bone, and position the implant prior to surgery.
- Navio System Handpiece - The Navio system handpiece controls the position of the Anspach Drill and bur relative to the position of the guard and the desired profile of the bone being cut. In exposure mode, as the bur nears the target surface of the bone intended to accept the implant, the Anspach drill and bur retracts into the guard to prevent further cutting of bone.

The Navio system is intended to assist the surgeon in providing software-defined spatial boundaries for orientation and reference information to anatomical structures during orthopedic procedures. The system is indicated for use in surgical knee procedures, in which the use of stereotactic surgery may be appropriate, and where reference to rigid anatomical bony structures can be determined. These procedures include UKR and patellofemoral arthroplasty. The Navio System is indicated for use with cemented implants only (refer to User Manuals for more detail).

#### **4.1. Surgical Technique**

The operative visit of this study is retrospective. The use of the Navio System was performed per standard of care at the participating study sites. The Navio System is indicated for all cemented Unicondylar Knee implants, therefore, all Unicondylar Knee cemented implant designs will be included in this study.

#### **5. STUDY POPULATION**

##### **5.1. Subject Screening and Enrollment**

To eliminate the potential for selection bias, Investigators will consecutively screen subjects by date of surgery, starting with their first Navio-assisted UKR subject. For screening, only information in the medical records will be reviewed. Subjects meeting all eligibility criteria will be listed on a Screening and Enrollment log.

Once a subject has completed the informed consent process, if required by the IRB/EC, the subject will be considered enrolled and assigned a consecutive Subject Identification (ID) number that identifies a single study knee. The subject ID number will be listed on the Screening and Enrollment Log. In the event that a subject has bilateral Navio assisted UKR, only the first treated knee will be enrolled and assigned a Subject ID. The Screening and Enrollment Log is the source in which records all screening and enrollment details are recorded.

## **5.2. Informed Consent**

Study sites will obtain IRB/EC approval for this study.

An IRB/EC waiver of informed consent for study participation should be requested for those subjects who meet eligibility criteria and have retrospectively completed a 2-year postoperative visit, are deceased, or are lost to follow-up, per IRB/EC policy. If allowed, a retrospective data set will be collected on these subjects. A copy of the waiver of informed consent will be placed in the subject file.

Subjects who meet eligibility criteria, are alive, and have not completed a 2-year postoperative visit, will be contacted and asked to provide Informed Consent prior to any retrospective or prospective data collection. These subjects may consent for participation only in the retrospective phase of the study or may consent for participation in both the retrospective and prospective phases of the study. The informed consent process will be documented in the subject's medical record and on the study Case Report Forms (CRFs). The informed consent form (ICF) will be placed in the subject file and a copy will be provided to the subject.

If a subject refuses participation, no further information will be collected. Reason for exclusion should be noted on the Screening and Enrollment Log.

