### **6.3. Prospective Data Collection: 2-Year (-3 months) or Greater Postoperative Follow-up**

Collect the following prospective data for subjects who have not retrospectively completed a 2-year (-3months) or greater postoperative visit and consent to participate in the prospective phase of the study:

- Implant Status
- KSS
- VR-12
- Anterior/Posterior and lateral radiographs and assessments:
  - Radiographic findings
  - Component orientation
  - Radiolucencies
  - Migration
  - Osteolysis
  - Stress shielding
  - Subsidence
- Revision CRF, if applicable
- End of Study CRF
- Study Device and Procedure-Related Adverse Events

The prospective follow-up visit may occur in an office or remotely. If completed remotely (e.g. telephone call, mailing of subject questionnaires and/or any other means), secondary endpoint data will be collected to the extent possible.

If the subject already completed the 2-year visit at the time of enrollment, 2-year visit data will be collected retrospectively as defined in section 6.2.

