#### F. Revisions

Subjects who have undergone a revision procedure of the study knee will be considered terminated from the study from the date of the revision. Study-related data will not be collected following the date of the revision. The appropriate CRFs will be completed for these subjects to document the details of study termination and revision.

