#### **9.1. Sample Size Calculation**

This study will screen and consent patients until a total of 128 subjects, from up to 10 sites, treated with the study device have been enrolled in the study.

The study is intended to test for non-inferiority in the percentage of revision-free survival at 2 years recorded during the study compared to existing literature. The Australian Orthopaedic Association National Joint Replacement Registry 2015 Annual Report (13) records the revision-free survival for at 2-years as 95.7%.

Using a non-inferiority margin of 7%, a sample size of 115 subjects will provide at least 80% power at the 5% significance level using exact binomial methods. To allow for a 10% attrition and drop-out rate, a total of 128 subjects will be enrolled.

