#### **9.2. Missing Data**

A complete accountability report, along with the explanation for lost-to-follow-up, death, revision, and withdrawn subjects is to be provided in the Clinical Study Report (CSR). The methods used to handle missing or incomplete data for the efficacy and safety measures will be detailed in the Statistical Analysis Plan (SAP).

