### **9.4. Analyses**

A formal SAP will be written and finalized prior to database lock. The SAP will detail the summaries and analyses to be performed.

- Primary endpoint:

The primary endpoint of the study is the Navio System assisted UKR revision rate at 2 years postoperatively. A one-sided 95% confidence interval for the revision [free] rate of the Navio System assisted UKR will be calculated using exact binomial methods. Non-inferiority, using a 7% non-inferiority margin will be declared if the lower bound of the confidence interval is  $>88.7\%$ . Time to occurrence of revision will also be analyzed using Kaplan-Meier survival analysis. Where appropriate, statistical modeling will be considered with prognostic and baseline factors adjusted for.

- Secondary endpoints:

Where appropriate, the secondary endpoints will be analyzed using either an ANOVA or Repeated Measures analysis, depending on whether a comparison between two time points or multiple time points is conducted. In each case, prognostic and baseline factors will be adjusted for. For endpoints where further analysis is not warranted, or not considered appropriate, tabulations detailing frequency distributions and/or summary statistics will be produced.

- Safety:

Numbers and types of AE, along with rates of AE types; with 95% confidence intervals for the rates (constructed using either exact binomial or asymptotic methods where appropriate) will be tabulated.

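### Where a consent waiver is granted, entry to the study can depend on whether the knee was revised, and no planned analysis looks at refusers

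*Protocol*

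**What the plan says.** Protocol 5.1 relies on screening order: "To eliminate the potential for selection bias, Investigators will consecutively screen subjects by date of surgery". Screening uses medical records only, and enrolment follows consent where the IRB/EC requires it.

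Protocol 5.2 and 10.3 then create two routes. A waiver is requested for eligible subjects who have completed a 2-year visit, are deceased, or are lost to follow-up (10.3 adds those who cannot be contacted). For the rest: "Subjects who meet eligibility criteria, are alive, and have not completed a 2-year postoperative visit, will be contacted and asked to provide Informed Consent" before any retrospective or prospective data are collected. On refusal: "If a subject refuses participation, no further information will be collected. Reason for exclusion should be noted on the Screening and Enrollment Log". Section 6.3 collects "prospective data for subjects who have not retrospectively completed a 2-year (-3months) or greater postoperative visit and consent to participate".

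Protocol 7.1 F ends participation at revision: "Study-related data will not be collected following the date of the revision". Protocol 9.1 sets the stopping point for enrolment: "This study will screen and consent patients until a total of 128 subjects".

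Protocol 10.3 says that the waiver, if allowed, reaches every patient who had the procedure and so removes selection bias. Its next paragraph requires a signed form from living patients without a 2-year visit.

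On analysis, Protocol 9.2 promises "A complete accountability report, along with the explanation for lost-to-follow-up, death, revision, and withdrawn subjects". SAP 7.6 tabulates completion, deaths, revisions and terminations. SAP 7.10 has one sensitivity analysis of the primary endpoint, in the per protocol population, which SAP 7.2 defines as a subset of the enrolled patients.

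**The concern.** The waiver route that most living patients would use is a completed 2-year visit. A patient revised before 2 years leaves the study at revision, so that patient will usually not have such a study visit. The route into the study is therefore linked to the primary outcome. Consecutive screening does not break the link, because the selection happens after screening, at consent.

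The documents do not say whether a clinic visit after revision counts as the 2-year visit. Sections 5.2 and 10.3 also do not repeat the 3-month window used in 6.3.

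The primary test sets one arm against a fixed 88.7%, so there is no concurrent control in which the same selection would cancel. If revised patients enter less often than unrevised patients, survivorship is too high and a false claim of non-inferiority becomes more likely. Refusers are replaced, and neither Protocol 9.2 nor SAP 7.6 names refusals before enrolment, so the report need not show that this had happened.

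**Working it through.** **1. Who enters by which route, where the waiver is granted (Protocol 5.2, 6.3, 7.1 F, 10.3)**

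| Patient | Route |
|---|---|
| Unrevised, 2-year visit on record | Waiver |
| Unrevised, alive, reachable, no 2-year visit | Consent |
| Revised before 2 years, alive, reachable, no later visit counted | Consent |
| Revised after a qualifying visit | Waiver |
| Deceased, lost or not contactable, revised or not | Waiver |

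Only the first row is open to unrevised patients alone. The second row and the last two rows weaken the link but do not remove it.

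**2. The plan's own figure.** Inputs from Protocol 9.1 and 9.4: reference survival 95.7%, margin 7 points, bound 95.7 − 7 = 88.7% (revision 11.3%), 115 evaluable. The rule is: "A one-sided 95% confidence interval for the revision [free] rate of the Navio System assisted UKR will be calculated using exact binomial methods".
- 7 revisions in 115 give a lower limit of 88.87% (pass); 8 give 87.80% (fail). Success means at most 7 revisions.
- False-positive rate: P(X ≤ 7 | 115, 0.113) = 0.0446.
- Power: P(X ≤ 7 | 115, 0.043) = 0.877, so the stated 80% holds. 115/0.9 = 127.8, giving 128.
- The exact analogue of the SAP's two-sided limit allows at most 6 revisions: false-positive rate 0.0201, power 0.774.

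**3. Effect of unequal entry.** Let k be the inclusion of revised patients, w the share of unrevised patients under waiver, and u = w + (1 − w)k the inclusion of unrevised patients. With true revision rate r,

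observed rate p = rk / (rk + (1 − r)u).

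The documents give neither k nor w. Assumed: k = 0.9/0.8/0.7 and w = 10%, 25% or 50%. At r = 11.3%, n = 115, one-sided exact rule (base 4.5%):

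| w | u | p | P(X ≤ 7) |
|---|---|---|---|
| 10% | 0.91/0.82/0.73 | 0.1119/0.1105/0.1089 | 4.8/5.3/5.9% |
| 25% | 0.925/0.85/0.775 | 0.1103/0.1071/0.1032 | 5.3/6.6/8.4% |
| 50% | 0.95/0.90/0.85 | 0.1077/0.1017/0.0950 | 6.3/9.2/13.6% |

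With at most 6 revisions allowed and w = 50%, the rate rises from 2.0% to 3.0/4.6/7.2%. If k = u, then p = r and nothing changes.

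At the design rate r = 4.3% with w = 50%, p = 4.08/3.84/3.57%, a shift of 0.22/0.46/0.73 points.

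**4. Tipping point.** Assume 5 revisions in 115 and 15 refusers, all added to the denominator (130).
- One-sided exact: 8/130 gives 89.17% (pass), 9/130 gives 88.23% (fail). The verdict changes when 4 of the 15 were revised.
- Two-sided exact: 7/130 gives 89.22% (pass), 8/130 gives 88.23% (fail). It changes at 3 of 15.

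These are binomial calculations. SAP 7.10 uses a Kaplan-Meier limit and does not say how its interval is built, so they approximate that test.

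**The case against.** The premise is partly inferred. Section 7.1 F stops study data at revision, whereas the waiver turns on whether a 2-year visit was completed, which is a fact in the medical record. If a clinic visit after revision counts, much of the asymmetry goes. This stands, and it is why the definition is the first thing to settle.

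The model also understates the entry of revised patients. Those who died, were lost, could not be contacted, or were revised after a qualifying visit can all enter under the waiver, so setting k equal to a consent rate treats too many of them as needing consent. Living unrevised patients without a 2-year visit must consent too. Both points stand, and with 10% waived the inflation is small.

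The tipping example points to some robustness. Under the 50% model at the design rate, the revised share of refusers is 0.043/(0.043 + 0.957 × 0.5) = 8%, or about 1.2 of 15, against the 3 or 4 needed.

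The plan is not blind to refusals: the log records reasons for exclusion, and the SAP 7.6 accountability list is open-ended. But no planned table or analysis uses the log. Section 8.1 G asks for all revisions to be reported, but for study knees, and a refuser has none.

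A reader might infer that the study will overstate survivorship, that its error rate is 13.6%, or that revised patients cannot have their charts read without consent. The documents support none of these. They give no consent rates or waiver share, and screening reads the records before consent. Only the collection of study data waits for it.

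**Conclusion.** The concern holds as a structural weakness of unknown direction and size. Where the waiver is granted, entry can depend on the primary outcome, the 10.3 statement that selection bias is removed is contradicted by the paragraph after it, and no planned analysis examines refusers. Where the waiver is refused and everyone must consent, the asymmetry largely disappears.

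Survivorship is biased upward only if revised patients are included less often than unrevised patients. The effect is small at the design rate and matters mainly if true survival is near 88.7%. Every figure for its size rests on the assumed waiver shares and inclusion rates. Severity is minor to moderate.

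**What to change.** 1. Correct the sentence in Protocol 10.3 that claims selection bias is removed. State in 5.2 and 10.3 that, for the waiver, a clinic visit at 2 years (−3 months) or later counts whether or not the knee was revised.
2. Add to SAP 7.6 the number of eligible patients who refused, by site, from the Screening and Enrollment Log, and the numbers entered by waiver and by consent.
3. Add to SAP 7.10 a tipping analysis of the 88.7% decision over a range of revision proportions among refusers, laid out as in step 4 of the working.
4. Optional, and for the IRB/EC to decide: request the waiver for retrospective implant-status data on all consecutively screened eligible patients. It should not cover revised patients alone. With all revised and 95/90/85% of unrevised patients included, a true 4.3% would appear as 4.52/4.76/5.02%, and power at n = 115 (one-sided exact) would fall from 0.877 to 0.850/0.818/0.779.

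The cost is a corrected sentence, a definition, a few table rows and one analysis, with no extra visits or patients. The conclusion may be a little less favourable. SAP 7.15 mentions 27 subjects already analysed, so item 4 may come late; items 2 and 3 need only log counts and assumed proportions.
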